1.2 Rationale

This is a non-interventional PASS in adults to investigate the safety and tolerability of ITULAZAX in the real-life setting in Germany, the Netherlands, Denmark, Sweden, Norway and Finland. The use of ITULAZAX is performed according to normal clinical practice and according to the SmPC. The number of patients to be included in the study will add to the existing safety data for ITULAZAX. The decision of the physician to prescribe SLIT with ITULAZAX is taken independently from the inclusion of the patient in the study.

2 Study objectives

2.1 Primary objective

The primary objective of the study is:

- To investigate the safety and tolerability of ITULAZAX in adults (18-65 years of age) allergic to tree treated with ITULAZAX in the first 4-6 months of treatment in a real-life setting.

3 Investigational plan

3.1 Overall study design

[figure not shown]
This is a non-interventional, observational, multi-site, open-label, multi-national PASS to investigate the safety and tolerability of ITULAZAX in adult patients in a real-life setting in Germany, the Netherlands, Denmark, Sweden, Norway and Finland.

A total number of approximately 1000 patients (aged 18-65 years) are planned to be enrolled and to be prescribed ITULAZAX in accordance with the nationally approved SmPC [5] and normal clinical practice.

The study will be initiated in November 2019 and the patients are planned to be followed for 4-6 (4 on average) months. A total number of 3-4 visits with approximately 1-3 months in between are planned (Figure 1).

The study is a non-interventional PASS based on the investigator's prescription of ITULAZAX, for which reason the number of visits and the duration between the visits are only intended as a guide.

Figure 1 Study design

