2	13 Jan 2020	2.0	
Table 2, Flow chart: Time frame V2, V3, V4 changed from 4-12 weeks to 1-3 months to be consistent with text above.
 
Study milestones) updated (Section 3.3 and Synopsis):
 
 - Planned last patient last visit changed from Oct 2021 to Jun 2022 - Planned final study report changed from Oct 2022 to Jun 2023. 
Section 2.1: Treatment period corrected from 4 to 4-6 months aligned with Section 3.1 and Synopsis.

3	29 Apr 2020	3.0	
 - Study milestones, Planned first patient first visit updated to “Mar 2020” (Section 3.3 and Synopsis). - List of abbreviations: “MAH, Marketing authorization holder” added. - Section 3.2.2 Secondary endpoints: bullet 5 and 6, observation period adjusted to: “... the first 4-6 months of treatment”. - Section 4.2 Collection, recording and reporting of adverse events: 
 - Local safety contact persons/Germany: “[name]” deleted and replaced by: “[name] and [name]. [name]” - Reference Safety information (RSI) document, changed to: “Assessment of expectedness of non-serious AEs and SAEs for submission purposes will be performed by the MAH according to the reference safety information which is the current approved Company Core Safety Information (CCSI). In case the CCSI is changed during the study, the expectedness assessment will be done acc. to the updated CCSI by the MAH. - Pregnancy: 2nd paragraph, 2nd sentence “observed by the investigator or reported by the subject must be recorded and evaluated via the AE form and reported to ALK within 14 days of obtaining knowledge

Template
TPL48761
Signature: OnPaper

NI Protocol

			of the event via the AE form provided in the eCRF." Deleted.
	28 May 2020	3.0	Section 4.2 Collection, recording and reporting of adverse events, paragraph "Reference Safety Information (RSI) document" deleted.
4	04 October 2022	4.0	Title page (page 1): Address of sponsor (street name) changed from: "[name]" to "[name]".

Flow chart

A total number of maximum 4 visits was planned during the study; visit 1 (baseline), visit 2 (1-3 months after visit 1), visit 3 (1-3 months after visit 2) and visit 4 (final visit, 1-3 months after visit 3). Please refer to the flow chart in Table 2 for a summary and timing of planned visits, and the procedures planned at each visit.

Table 2 Flow chart

Visit ID	V1	V2	V3	V4

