3.2 Endpoints

3.2.1 Primary endpoint

Sum of pre-specified local adverse drug reactions (including lip swelling/oedema, mouth oedema, palatal oedema, swollen tongue/oedema, oropharyngeal swelling (oedema, pharyngeal oedema/throat tightness), laryngeal oedema).

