3.2.2 Secondary endpoint(s)

- Number of treatment related AEs
- Number of systemic reactions
- Number of non-local adverse drug reactions
- Number of serious AEs (SAEs)
- Sum of pre-specified local adverse reactions (as specified in the primary endpoint) within the first 4-6 months of treatment in patients with history of Pollen Food Syndrome (PFS)
- Adherence to the first 4-6 months of treatment.

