3.4 Discussion of design

Aim of the study is to gain information on safety and tolerability and to confirm the known safety profile of ITULAZAX from the clinical development program within a real-life setting.

As this is a non-interventional PASS, potential confounding factors cannot be ruled out. Data collection will reflect routine clinical practice rather than mandatory assessments at pre-specified time points. This may have an impact on the amount of data and the interpretation. Since this is an open-label design, the knowledge of active treatment may affect both investigator-perceived and patient-reported data. The recording of data by physicians in an eCRF allows immediate access to the data and processing of queries.

The strength of the study is that it is able to generate data on safety and tolerability for treatment with ITULAZAX in the real-life setting and in real-life patients with demographics and disease-related characteristics consistent with populations seen in clinical practice.

The sum of pre-specified local adverse drug reactions (including lip swelling/oedema, mouth oedema, palatal oedema, swollen tongue/oedema, oropharyngeal swelling (oedema, pharyngeal oedema/throat tightness, laryngeal oedema) as primary endpoint and number of treatment-related AEs, number of systemic reactions, number of non-local reactions, number of

Template
TPL48761
Signature: OnPaper

serious AEs (SAEs), sum of pre-specified local adverse drug reactions within the first 4 months of treatment in the group of patients with data on Pollen food syndrome (PFS) and adherence to the first 4 months of treatment are suited to address the safety and tolerability in real-life as objective of the study

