- If applicable and done in routinely use: Antibody Responder Test (ART), (ART generally applied, if yes results IgE, IgG4, neg./pos., ART score)
- First administration of other SLIT-tablets, allergen 1, allergen 2 (date/time of application, anti-allergic premedication applied (no/yes), AEs (no/yes, if yes document on AE pages), if applicable
- Schedule date for visit 4 (if applicable)

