4.2 Collection, recording and reporting of adverse events

All AEs are systematically collected in this study from the patient has signed informed consent and until end of study defined as last visit 4. These events must be recorded and evaluated via the AE form in the eCRF by the investigator. The investigator should record the diagnosis if available and if not available the symptoms should be recorded separately.

Specific additional reporting requirements are applicable for SAEs and pregnancy related events as further described below. The additional information must be provided according to requested timelines by fax/email to the local affiliate of ALK via:

	Germany	Denmark, Norway, Sweden, Finland	Netherlands
E-Mail	[contact]	[contact]	[contact]
[contact]	[name]	[name]
Emergency [contact]	DK: [name] NO: [name] SE: [name] FI: [name]	[name]
Local safety contact persons	[name], Stufenplanbeauftragte [name], [name]. [name] (beide stellv. Stufenplanbeauftragte)	[name], NPPV [name], deputy NPPV	[name], NPPV [name], [name], deputy NPPVs

If requested, please forward supporting documents to ALK via fax or via e-mail to the appropriate local affiliate (contact details see above). Please state the trial ID (NI-TT-01) and the subject and site ID on all documents.

IMPORTANT: Any information that could reveal the identity of the trial subject must be hidden or removed in the source documentation. Also, information that is not relevant for the subject and the subject's condition must be hidden or removed.

ALK informs the competent authorities and independent ethics committees (IECs) about AEs reported in the study in accordance with local requirements in force.

SAEs

- All SAEs must be reported to ALK via the SAE form provided in the eCRF within 24 hours of obtaining knowledge of the event.
- SAEs must be followed until the outcome of the event is "recovered", "recovered with sequelae", "death" and until all queries have been resolved. For cases of chronic conditions and cancer, follow-up until "recovered", "recovered with sequelae" or

Template
TPL48761
Signature: OnPaper

NI Protocol

“death” is not required. After the subject has completed the study, these cases can be closed with “not recovered”.

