7.4 Safety analysis

AEs as well as breakdown of AEs and treatment-related AEs (possibly related) according to seriousness, severity and causality will be summarised for AEs during administration (V1 to V4).

AEs will be summarised by MedDRA System Organ Classes and MedDRA Preferred Terms displaying number of patients, frequency of patients having AEs as well as number of AEs.

Missing data will not be replaced.

8 Protection of human subjects

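### The stated follow-up of 4-6 months does not match the visit schedule, and the primary endpoint and adverse event analysis are not tied to one observation window

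*Protocol*

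**What the plan says.** Protocol section 3.1 says patients are planned to be "followed for 4-6 (4 on average) months. A total number of 3-4 visits with approximately 1-3 months in between", and adds that visit number and spacing serve only as a guide. The text above the flow chart (Table 2) repeats the spacing: "visit 2 (1-3 months after visit 1), visit 3 (1-3 months after visit 2) and visit 4 (final visit, 1-3 months after visit 3". Table 2 allows 10 days either side of each visit.

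The observation period is then described in several ways:

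- **Primary objective (2.1):** the first 4-6 months of treatment.
- **Primary endpoint (3.2.1):** "Sum of pre-specified local adverse drug reactions", followed by a list of reactions and no time limit.
- **Secondary endpoints (3.2.2):** the pollen food syndrome endpoint is counted "within the first 4-6 months of treatment in patients with history of Pollen Food Syndrome (PFS"; adherence also refers to the first 4-6 months.
- **Discussion of design (3.4):** the same two endpoints are given 4 months, for example "adherence to the first 4 months of treatment".
- **Safety analysis (7.4):** adverse events "will be summarised for AEs during administration (V1 to V4", shown as numbers of patients, percentages of patients and numbers of events.
- **Adverse event collection (4.2):** from consent "until end of study defined as last visit 4". The visit 3 procedures (3.7.3), however, read "Schedule date for visit 4 (if applicable", so a patient may finish at V3.

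**The concern.** Both the number of reactions and the percentage of patients with a reaction can only rise as observation lengthens. If the period is not fixed, the headline result depends partly on how sites space their visits, on whether V4 takes place and on who leaves early. It also need not describe the 4-6 months named in the objective.

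Section 3.4 says the study should confirm the safety profile known from clinical development, and section 1.1 points to expected frequencies in the product information. A frequency over an unstated and variable period is a weak basis for that comparison. Section 9.3 requires the primary publication to be analysed as the protocol stipulates, so the protocol's wording carries weight.

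**Working it through.** **Inputs.** 3 or 4 visits, 1-3 months per gap (section 3.1 and flow chart text); 10 days either side of a visit (Table 2); stated follow-up 4-6 months, 4 on average (section 3.1).

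**Step 1: follow-up permitted by the schedule.** Follow-up = (visits − 1) × gap.

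| Visits | Gaps | Shortest | Midpoint | Longest |
|---|---|---|---|---|
| 3 | 2 | 2 × 1 = 2 months | 2 × 2 = 4 | 2 × 3 = 6 |
| 4 | 3 | 3 × 1 = 3 months | 3 × 2 = 6 | 3 × 3 = 9 |

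The overall range is 2-9 months. Ten days is 10/30.44 = 0.33 month, so the window on the last visit alone widens this to about 1.7-9.3 months. The stated 4 and 6 are reproduced only as the two midpoints. The longest scheduled period is 9/2 = 4.5 times the shortest, against 6/4 = 1.5 times for a true 4-6 month range.

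**Step 2: the stated average.** If a share p of patients had 6 months and the rest 4, the mean would be 4 + 2p. It equals 4 only if p = 0. Any patient above 4 months, with none below, pulls the mean above 4.

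**Step 3: gaps needed to land in 4-6 months.** With three visits the average gap must be 4/2 to 6/2 = 2.0-3.0 months; with four visits, 4/3 to 6/3 = 1.33-2.0 months. The guide of 1-3 months does not ensure either.

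**Step 4: illustration of spread (assumption: independent gaps, uniform on 1-3 months).** Three-visit patients average 4.0 months, with 50% below 4 and 50% within 4-6. Four-visit patients average 6.0 months, with 2% below 4, 48% within 4-6 and 50% above 6.

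**Step 5: illustration of effect (assumption: 10% of patients have a first reaction by 4 months).**

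- *Constant rate.* Rate = −ln(0.9)/4 per month; cumulative incidence = 1 − 0.9^(t/4).
- *Front-loaded.* 9 of the 10 percentage points fall in month 1, then a constant rate of ln(0.91/0.90)/3 = 0.00368 per month; cumulative incidence = 1 − 0.91 × exp(−0.00368 × (t − 1)).

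| Months observed | Constant rate | Front-loaded |
|---|---|---|
| 2 | 5.1% | 9.3% |
| 4 | 10.0% | 10.0% |
| 6 | 14.6% | 10.7% |
| 9 | 21.1% | 11.6% |

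The protocol gives neither rates nor onset timing, so it does not say which column is closer to the truth.

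**The case against.** The strongest reply is that this is a non-interventional, single-arm, descriptive study. Section 3.1 calls the visits a guide, and section 3.4 warns that data follow routine practice and that this may affect interpretation. The figures 4 and 6 match the schedule midpoints, the objective supplies a period, and no between-group comparison can be biased. Person-time and censoring are often left to a statistical analysis plan, which is not at hand.

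Much of this stands. Flexible visits are appropriate, and the lack of exposure-adjusted methods would not be a finding by itself. But if the visits cannot enforce a period, the endpoint definition has to. The objective's period is itself a range, is not carried into sections 3.2.1 or 7.4, and conflicts with section 3.4. The amendment log shows that 4-6 months was introduced on purpose in sections 2.1 and 3.2.2, so the 4 months in section 3.4 may simply not have been updated; it is still current text.

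A reader might infer more than the documents support:

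- **That about half of patients will miss the 4-6 month period.** This needs independent uniform gaps. Because V4 is optional, sites could choose visits to meet the target. The documents support neither pattern.
- **That incidence could range from 5% to 21%.** This needs a constant rate and compares the two extremes. At the midpoints of 4 and 6 months the same model gives 10.0% and 14.6%, and front-loading nearly removes the contrast.
- **That patients lost after V1 count as event-free.** Reactions after the first intake are assessed at V1 (3.7.1), and outstanding data are sought on discontinuation (3.5.2). Such patients keep the events recorded; only unrecorded later events are missed.

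**Conclusion.** The point holds at moderate severity. The arithmetic and the conflicts between sections rest on the protocol alone: a permitted follow-up of 2-9 months against a stated 4-6, an average that the stated range cannot have, no window on the primary endpoint, two windows for the same two secondary endpoints, and an end of adverse event collection tied to an optional visit. Followed as written, section 7.4 could put events from as late as about 9 months, over unequal observation, into a result meant for the first 4-6 months.

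The 2-9 months is what the schedule permits, not what most patients are expected to have. The numerical effect on the primary endpoint cannot be determined from the protocol. It would be small if reactions cluster at the start of treatment and larger if they continue at a steady rate. A more severe rating is not warranted for a descriptive study without formal tests.

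**What to change.** 1. In section 3.1, state the follow-up that the schedule permits and correct the average.
2. Apply one fixed analysis window, counted from first intake, in sections 3.2.1, 3.2.2, 3.4 and 7.4: for example to the end of month 6, with a 4-month result alongside. List later events separately.
3. In section 4.2, define the end of adverse event collection as the patient's own last visit (V3 or V4) or withdrawal.
4. Beside the crude counts, show total person-time and the cumulative incidence of first event, censored at last contact. Cumulative incidence is the safer summary if reactions are front-loaded, since a single rate per person-month could then mislead.
5. Confirm that the eCRF records adverse event onset dates; the protocol lists the date and time of first intake but does not name onset dates. Censor at treatment stop only if that date is recorded. The listed procedures name intake frequency and reasons for not taking the tablet or discontinuing, but no stop date.

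The cost is wording and a little more analysis. No visit or treatment has to change.

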3.2 Endpoints

3.2.1 Primary endpoint

Sum of pre-specified local adverse drug reactions (including lip swelling/oedema, mouth oedema, palatal oedema, swollen tongue/oedema, oropharyngeal swelling (oedema, pharyngeal oedema/throat tightness), laryngeal oedema).

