In general, treatment was well tolerated. The most frequently reported treatment-related adverse events (TRAEs) were mild-to-moderate local reactions related to sublingual administration of the tablet, the most common events were oral pruritus and throat irritation. Twenty-five (8%) subjects in ITULAZAX group discontinued the trial because of 98 AEs. These were mainly characterised as irritation or swelling in the mouth or throat of mild or moderate intensity.

The safety and tolerability during routine treatment in real life will be investigated in this Non-interventional-PASS.

The safety and tolerability profile and expected frequencies according to the clinical trials with ITULAZAX are described in the Summary of Product Characteristics (SmPC), [5].

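### The primary endpoint is an event total with no patient-level unit or denominator, and section 7.4 plans no patient frequency for the pre-specified composite

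*Protocol*

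**What the plan says.** Section 3.2.1 gives the primary endpoint as "Sum of pre-specified local adverse drug reactions (including lip swelling/oedema, mouth oedema, palatal oedema, swollen tongue/oedema, oropharyngeal swelling", with the list running on to laryngeal oedema. Section 3.4 repeats the definition and judges it suitable for the objective. Neither place says whether repeat reactions, or several listed terms in one patient, count once or more than once. Section 3.2.1 names no denominator and no time window.

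In 3.2.2, four secondary endpoints are numbers of events (treatment-related AEs, systemic reactions, non-local reactions, SAEs), for example "Number of systemic reactions". A fifth is the same sum in patients with a history of pollen food syndrome (PFS). Only the sixth, adherence, is not an event total.

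The stated aim in 3.4 is "to confirm the known safety profile of ITULAZAX from the clinical development program within a real-life setting". Section 1.1 says that the "expected frequencies according to the clinical trials with ITULAZAX are described in the Summary of Product Characteristics".

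For the analysis, 7.2 defines the Safety Set as all patients who took at least one dose. Section 7.4 plans a breakdown of AEs and treatment-related AEs by seriousness, severity and causality, and then tables by System Organ Class and Preferred Term "displaying number of patients, frequency of patients having AEs as well as number of AEs". Section 7.1 makes everything descriptive, without tests or a sample size calculation. Section 4.2 has the investigator enter a diagnosis where there is one and otherwise each symptom as its own record.

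**The concern.** The unit of the primary endpoint does not match the unit of the profile it is meant to confirm. The reference profile is expressed as frequencies, while the endpoint is a count of reactions. To get from one to the other, the reader must know how many patients contributed to the count, and no planned output named in the protocol gives that number for the pre-specified group of reactions.

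Two features make this more than a matter of wording. First, the count is sensitive to recording practice. Under 4.2, a patient with lip, tongue and throat swelling may generate one record or three, depending on whether a diagnosis is entered. The planned 170 to 178 investigators in six countries (50 + 80 + 4 × 10 up to 50 + 80 + 4 × 12) need not all do the same. Whether a patient had at least one listed reaction is much less affected by such splitting.

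Second, the tables in 7.4 do not fill the gap. That patient would appear in three Preferred Term rows, so adding rows overcounts patients. A System Organ Class row does not isolate the pre-specified list.

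At stake is whether the main result can be read as a patient risk and compared with what is already known.

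**Working it through.** **Figures in the plan.** Section 7.1 says that no sample size calculation was done, so there is none to reproduce for the 1000. One safety figure can be checked: "Twenty-five (8%) subjects in ITULAZAX group discontinued the trial because of 98 AEs". TT-04 randomised 634 subjects 1:1, so about 317 per arm, and 25/317 = 7.9%, which agrees with the stated 8%. The same sentence gives 98/25 = 3.92 AEs per affected subject.

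**Inputs for the illustration.** n = 1000 (7.1, planned size). Reactions per affected patient, m, is an assumption from 1 to 3.92. The upper value comes from subjects who left TT-04 because of AEs, a group selected for poor tolerance, and their AEs are not the same as the list in 3.2.1. It shows how far events and patients can diverge. It does not estimate m for this endpoint.

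**From total to patients.** Affected patients x = S/m, where S is the total. The exact (Clopper-Pearson) 95% limits are the 2.5% quantile of Beta(x, n − x + 1) and the 97.5% quantile of Beta(x + 1, n − x).

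| Total S (assumed) | m (assumed) | Patients x | Risk | Exact 95% CI |
|---|---|---|---|---|
| 98 | 1 | 98 | 9.8% | 8.0-11.8% |
| 98 | 3.92 | 25 | 2.5% | 1.6-3.7% |
| 200 | 1 | 200 | 20.0% | 17.6-22.6% |
| 200 | 2 | 100 | 10.0% | 8.2-12.0% |
| 200 | 3.92 | 51 | 5.1% | 3.8-6.7% |

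Within each total, the intervals at the two ends do not overlap. The same reported sum fits an almost fourfold range of patient risk (9.8/2.5 = 3.92).

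**Can Preferred Term rows recover the composite?** For any set of terms, the largest single frequency ≤ the frequency of any term ≤ the sum of the frequencies. With six terms at an assumed 5% each, the composite lies between 5% (full overlap) and 6 × 5% = 30% (no overlap). The rows do not fix it.

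**Can the data recover it?** Yes. AEs are entered per patient in the eCRF (4.2), with causality graded as possible or unlikely (4.1.3), and 7.2 supplies the denominator. A flag for at least one listed, possibly related reaction gives x directly. At n = 1000 the precision is useful: 5% gives 3.7-6.5%, 10% gives 8.2-12.0% and 20% gives 17.6-22.6%. If no patient has a systemic reaction, the upper limit is 1 − 0.025^(1/1000) = 0.37%.

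**The case against.** The strongest reply is that nothing is lost. Patients, AEs and causality are all recorded, the Safety Set is the natural denominator, and 7.4 already commits to patient frequencies alongside event counts. The first sentence of 7.4 also covers treatment-related AEs and serious AEs above the level of individual terms. Intervals, counting rules and table layout commonly belong in a statistical analysis plan, which is not available here. The study is descriptive, and no test or decision rule depends on the endpoint's unit.

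Much of this stands. The absence of a confidence interval is not a finding in itself. The overlap problem applies to the pre-specified local composite, its PFS subgroup and the systemic and non-local groupings. It applies less to treatment-related and serious AEs, although 7.4 does not say which statistic their breakdown will show.

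It is also right that the TT-04 figures come from a selected group. The 8% is a discontinuation rate, not a frequency of local reactions, so it is not the benchmark to be confirmed.

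What does not stand is that the analysis plan could simply settle the matter. The unit of the primary endpoint is fixed in 3.2.1 as a sum and repeated in 3.4. An analysis plan that reported a patient proportion as primary would be changing the endpoint, not detailing it.

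**Conclusion.** The point holds as a weakness in definition with a cheap remedy. As worded, the primary endpoint is an event total without a patient-level unit or denominator, and the protocol names no patient-level summary of the composite. The main result cannot be compared directly with a profile given as frequencies. In the illustration, one total of 98 reactions fits risks from 2.5% to 9.8%. That range rests on the assumed 1 to 3.92 reactions per affected patient and on 1000 treated patients. The true spread for this endpoint is unknown and could be narrower.

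A reader might go further and infer that the study cannot yield a patient risk with its uncertainty, or cannot confirm the known profile at all. The documents do not support that, because the per-patient eCRF records and the Safety Set are sufficient for both. A reader might also take 3.92 as the expected clustering of these reactions and widen the uncertainty accordingly. That is not supported either, because the figure describes AEs in subjects who discontinued TT-04.

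Because no data are lost and no test depends on the unit, this is a worthwhile improvement and not a flaw that invalidates the study.

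**What to change.** In 3.2.1, and to match in 3.4, define the primary endpoint as the number and percentage of Safety Set patients with at least one pre-specified local reaction possibly related to treatment during the first 4-6 months, with an exact (Clopper-Pearson) 95% interval. Keep the event sum and the events per affected patient as supportive summaries.

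In 3.2.2, report the PFS-subgroup, systemic and non-local reaction endpoints in the same way, using treated patients with a history of PFS as the denominator for the PFS endpoint.

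In 7.4, add a row or table for patients with any pre-specified local reaction, so that the composite does not have to be inferred from Preferred Term rows.

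This needs no new data, visits or hypothesis test and fits the descriptive design in 7.1. The cost is revised endpoint wording, one more table and a result that shows its interval.
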